6.0 Statistical **Methodology**

Treatment Assignment

Treatment assignment will be determined with the use of a randomization schedule that will utilize blocks to ensure approximate treatment balance at any time during the study enrollment phase.

Sample Size Determination

Sample size was determined with the use of historical unpublished data of Harris Hip parameters at 6 weeks post-operatively from patients who underwent the primary THA using the anterior surgical approach. The percentage of patients at 6 week post-operative that had the ability to climb stairs normally, and walk unlimited, were 37%, and 40% respectively. Using a 2-tailed Fisher's Exact test and assuming a difference in clinical results of 30% and statistical power of 85% the required sample size for this study is 40 patients per treatment group. To account for 10% attrition the sample size was increased to 44 patients per treatment group (88 patients total).

Primary Endpoint

The proportion of patients with the ability to climb stairs normally or walk unlimited at 6 weeks post-operatively is the primary endpoint in this study. However, the HOOS patient self-assessment dimensions of Pain, Symptoms, Activities of Daily Living, Sport & Recreation, and Quality of Life will be important secondary endpoints. Six minute walk test distances and VAS Pain scores are also secondary endpoints

Analysis Populations

The Intent-to-Treat population will be analyzed.

Interim Analyses

No formal interim analyses will be conducted.

Analyses Planned

Demographics of the 2 treatment groups and pre-operative Harris Hip Evaluation sub-scores and HOOS sub-scores will be compared using appropriate statistical methodologies to determine comparability of treatment groups pre-operatively.

The proportion of patients able to climb stairs normally or walk unlimited as evaluated with the Harris Hip Evaluation at 6 weeks post-operatively will be compared using a 2-tailed Fisher's Exact test. Potentially covariates (e.g. age, BMI, gender) will be assessed using logistic regression techniques.

IIS Clinical Research Agreement
[name]
January 28, 2013

HOOS sub-scores of Pain, Symptoms, Activities of Daily Living, Sport & Recreation, and Quality of Life will be scored according to the HOOS Users Guide and will be compared using parametric or non-parametric techniques (as appropriate) at 6 weeks, 3, 6 and 12 months post-operatively to determine if there is a difference between treatment groups and at what time points the difference are detected.

Six minute walk test distances at 6 weeks and 3 months and VAS Pain scores will also be compared using parametric or non-parametric techniques (as appropriate) at 6 weeks, 3, 6, 12 months, 24 months and 60 months post-operatively to determine if there is a difference between treatment groups and at what time points the difference are detected.

The prevalence of both inter-operative and post-operative complications and adverse events such as dislocation, hospital re-admission, revision operation, and other postoperative events not normally associated with THA will be compared between groups using a Fisher's Exact (2-tailed) test, with $p \leq 0.05$ being considered significant.

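### The 85% power reproduces for one Harris item (40% v an inferred 10%), but the primary test is on an either-item proportion with no stated rate, so 85% is not established for it

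*Combined protocol and SAP*

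**What the plan says.** All the relevant text is in section 6.0 of the combined protocol and SAP.

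- **Sample Size Determination, source:** the inputs are "historical unpublished data of Harris Hip parameters at 6 weeks post-operatively from patients who underwent the primary THA using the anterior surgical approach".
- **Sample Size Determination, rates:** the percentages with the "ability to climb stairs normally, and walk unlimited, were 37%, and 40% respectively". These are two items, each with its own rate.
- **Sample Size Determination, effect and test:** "Using a 2-tailed Fisher's Exact test and assuming a difference in clinical results of 30" per cent, leading to "statistical power of 85% the required sample size for this study is 40 patients per treatment group". The number is then raised to 44 per group (88 in total) for 10% attrition.
- **Primary Endpoint:** "The proportion of patients with the ability to climb stairs normally or walk unlimited at 6 weeks post-operatively is the primary endpoint".
- **Analyses Planned:** the same single quantity, "The proportion of patients able to climb stairs normally or walk unlimited as evaluated with the Harris Hip Evaluation", is compared with one two-tailed Fisher test.

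The plan gives no rate for the either-item proportion, no posterior-approach rate on any scale, no direction for the 30% and no significance level for the primary test. The only stated level, 0.05, belongs to the complications comparison, which "will be compared between groups using a Fisher's Exact (2-tailed) test".

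**The concern.** The quantity that was sized and the quantity that will be tested are not the same. A patient counts as a success on the primary endpoint by meeting either item, so the anterior success rate is at least the larger of the two item rates and may be well above it. The power to detect a fixed absolute difference depends on where the two proportions lie, and it falls as they move towards the middle of the scale. A power figure for a single item at 40% therefore does not carry over to the combined proportion without a rate for that proportion.

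What is at stake is how the primary result is read. If the comparison is not significant, readers will set it against a stated 85%, and the plan has not derived that figure for the quantity tested.

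**Working it through.** **Inputs from the plan:** anterior item rates 0.37 (stairs) and 0.40 (walking); difference 0.30; two-sided Fisher exact test; 40 per group, 44 with attrition.

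**Assumptions:** alpha 0.05 for the primary test; the 30% is an absolute difference; both item rates come from the same historical patients.

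**Formula.** With n per group and true rates pA (anterior) and pP (posterior), power = Σx Σy Bin(x; n, pA) · Bin(y; n, pP) · 1[Fisher two-sided p(x, y) ≤ 0.05], summed over all x and y from 0 to n.

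**Step 1: reproduce the plan's figure.**
- Walking item, posterior lower: 0.40 − 0.30 = 0.10. Power is 84.0% at n = 39 and 85.2% at n = 40, so 40 is the smallest n reaching 85%.
- Stairs item, posterior lower: 0.37 − 0.30 = 0.07. Power is 89.4% at n = 40.
- Walking item, posterior higher: 0.40 + 0.30 = 0.70. Power is 72.5% at n = 40, and 85% is first reached at n = 52.
- A relative 30% reduction (0.40 × 0.70 = 0.28) would give only about 14%, so the absolute reading is the one that fits.

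The stated 40 at 85% therefore matches one item at 40% v 10%. The 10% is inferred; the plan does not state it.

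**Step 2: bound the anterior either-item rate.**
- Lower bound, every stair climber also walks unlimited: max(0.37, 0.40) = 0.40.
- Upper bound, no overlap: 0.37 + 0.40 = 0.77.
- Independence, for illustration: 1 − 0.63 × 0.60 = 0.622.

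**Step 3: a 30-point posterior deficit on the either-item proportion.**

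| Anterior v posterior | Power, n = 40 | Power, n = 44 |
|---|---|---|
| 40 v 10 | 85.2% | 87.9% |
| 45 v 15 | 79.3% | 83.2% |
| 50 v 20 | 74.9% | 80.2% |
| 62.2 v 32.2 | 72.4% | 73.5% |
| 65 v 35 (lowest) | 72.4% | 73.2% |

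Over the whole 40-77% range this is 72-85% at 40 per group and 73-88% at 44. At 40 per group, 85% holds only up to an anterior rate of 40.1%. If f is the share of stair climbers who also walk unlimited, the anterior rate is 0.40 + 0.37(1 − f), so 0.401 needs f = 1 − 0.001/0.37 = 99.7%. At 44 per group the limit is 42.8%, or f = 1 − 0.028/0.37 = 92.4%.

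**Step 4: the 30 points applied to each item.** The posterior items become 0.10 and 0.07, so the posterior either-item rate lies between max(0.10, 0.07) = 0.10 and 0.10 + 0.07 = 0.17. Power at n = 40:
- Independence in both arms: posterior 1 − 0.93 × 0.90 = 0.163. For 62.2 v 16.3, 98.8%.
- Full overlap in both arms: 40 v 10, 85.2%.
- Full overlap in the anterior arm, slightly less in the posterior arm: 40 v 11, 81.6%.
- Full overlap in the anterior arm, none in the posterior arm: 40 v 17, 54.6%.

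The documents give no overlap in either arm. These cases show that the answer can go either way; they are not estimates.

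**The case against.** **The calculation is correct.** It is, for one item, and someone who sees the mismatch might wrongly infer an arithmetic error. The documents do not support that: 40 is exactly the smallest number reaching 85% at 40% v 10%.

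**The plan may be conservative.** If the 30 points were meant for each item, as the item-level sizing suggests, and overlap is similar in both arms, the either-item difference is 30 points or more and 85% is roughly a floor. This stands as a possibility. It rests on equal overlap, which the plan neither states nor supports, and a small departure (40 v 11) already takes power below 85% at 40 per group.

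**The direction can be recovered.** Largely so: on the two stated item rates, 40 per group fits only a lower posterior rate. That is why the main figures here use a posterior deficit. It remains an inference, since by symmetry 60 v 90 also gives 85.2%, although no 60% appears in the plan.

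**'Or' may mean two alternative items.** The endpoint and analysis text both speak of a single proportion and a single test. If two items were meant, the plan does not say which is primary.

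**Planned power matters little once results are in.** The estimate and its confidence interval should carry the interpretation. That limits the consequence, but the stated justification for the sample size should still refer to the endpoint tested. The missing alpha is minor, since 0.05 is used for the same test on complications.

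**Conclusion.** The point holds as a mismatch between the sizing assumption and the endpoint, and it should be fixed. The 85% belongs to a single item at 40% v an inferred 10%. For the either-item proportion, a 30-point posterior deficit has 72-85% power at 40 per group and 73-88% at 44; at 40 per group, 85% requires nearly every stair climber also to walk unlimited. If the 30 points apply to each item, the documents do not determine the power.

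A reader might go further and infer that the trial is underpowered. The documents do not support that: they lack the either-item rate, the posterior rate and the overlap, and some consistent assumptions give power well above 85%. The supported conclusion is that the 85% is not established for the primary test.

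This rests on alpha 0.05 for the primary test, an absolute 30-point difference, and both item rates coming from the same patients. The mismatch itself depends on none of these; the figures do.

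**What to change.** Keep the 88 patients, the endpoint and the Fisher test. Before the primary analysis:

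1. Tabulate the either-item rate from the historical anterior dataset that supplied the 37% and 40%.
2. In Sample Size Determination, state that rate, the assumed posterior rate, the direction and alpha, all for the combined proportion.
3. Replace the 85% with the exact Fisher power for those inputs at 40 and 44 per group, whichever way it moves.
4. If the rate cannot be tabulated, say that 85% applies to a single item at 40% v 10%, and that a 30-point deficit on the combined endpoint has 72-85% power at 40 per group (73-88% at 44).
5. If two alternative items were intended, name the primary one.

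The cost is one tabulation of data already used for the sizing and a few sentences of text, with no extra patients. The downside is that the stated power may become less favourable.

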The second surgical technique used in the study will be the posterior approach. This approach uses a standard OR table with the patient placed in the lateral decubitus position. A 12-14cm skin incision is utilized over the posterior-lateral corner of the hip. The gluteus maximus muscle is split in line with its fibers and the posterior capsule is opened. The hip is dislocated posteriorly and a femoral neck osteotomy is performed. The acetabular and femoral components are inserted in the same manner as is done with the anterior approach with press-fit fixation utilized. The posterior approach is well described in all major texts on Orthopedic Surgery. To minimize selection bias the surgical technique will be determined by a randomization schedule.

Radiographs and clinical data will be gathered for each qualifying patient in the manner outlined in the Study Procedures below. Harris Hip Evaluation scoring will be used to evaluate pain, function, activity levels, deformity, and range of motion. The HOOS patient reported outcomes will be used to evaluate function and pain relief.

Deaths, device, and procedure related complications will be reported.

Data to be collected includes, but is not limited to that specified in Section 5.2 below.

The primary focus of the study is to compare the short-term safety, efficacy and return to function of patients undergoing primary total hip arthroplasty utilizing an anterior approach vs a posterior approach. Upon completion of the study, a summary of the results will be submitted for publication.

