5.0 Data Collection

5.1 Pre-operative Data Collection

Subject ID
Date of Birth
Gender
Height
Weight
BMI
Left or right hip
Diagnosis

IIS Clinical Research Agreement
[name]
January 28, 2013

Harris Hip Score Elements
Set of x-rays
Pre-op hematocrit and hemoglobin
Timed walking test

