5.3 Post-operative Data

Pain scores pre and post administration of pain meds
Amount of pain medication required
Blood loss from drains over 36 hours post op
Hemoglobin / hematocrit on POD # 1&2
Functional activities (distance walked, transfers and assistive devices used)
Length of hospital stay
Harris Hip Score Elements
HOOS
Timed walking tests
Complications/Patient Withdrawal/Revision/Deaths (as applicable)

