The investigator will offer to answer any questions the Subject may have. If the Subject agrees to participate in the investigation, then the Subject must sign and date the IPC form prior to the day of surgery. However, if the IPC is signed on the day of surgery, then the source document must state that the Subject was given adequate time prior to the time of surgery to review and give consent. In such a case, the time the Subject signed the IPC form must be documented.

The original IPC form remains with the clinical investigator (i.e., within the CRF booklet or clinic chart) and a copy is provided to the Subject. The IPC is not forwarded to the Sponsor. Instead, the Investigator will complete the "Assurance of Investigator" form documenting that informed consent has been properly obtained and then submit a copy to the Sponsor. Once a Subject has executed the IPC documentation, they are considered a study Subject.

Post-operative visit schedule will consist of the following: pre-op, operative, and post-operatively at 2 weeks, 4-6 weeks, 3 months, 6-months, 12-months, 24 months and 60 months.

Time

2 weeks (7-21 days)

Data Collected

Average Pain Score (VAS)

Amount of pain MED use/day

Walking Distance

Use of Assistive Device

IIS Clinical Research Agreement
[name]
January 28, 2013

4-6 weeks (22-45 days)	Average Pain Score (VAS) Average pain MED use/day Walking distance Assistive Device X-ray Protocol cup position stem position limb length offset Return to work/Activity/Driving Timed Walking Test Harris Hip Score HOOS
3 months (60-120 days)	Pain Score (VAS) Average pain MED use/day Walking distance Assisted device Timed Walking Test Harris Hip Score HOOS
6 months (130-240 days)	Average Pain Score (VAS) Harris Hip Score HOOS
12 months (270-425 days)	Average Pain Score (VAS) Harris Hip Score X-ray Protocol HOOS
24 months (426-1460)	Average Pain Score (VAS) Harris Hip Score X-ray Protocol
60 months (1461-2737)	Average Pain Score (VAS) Harris Hip Score X-ray Protocol

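### Section 6.0 plans a comparison of pre-operative HOOS sub-scores, but no part of the protocol schedules HOOS before surgery

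*Combined protocol and SAP*

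**What the plan says.** Section 6.0 (Analyses Planned) commits to a check of baseline comparability: "pre-operative Harris Hip Evaluation sub-scores and HOOS sub-scores will be compared using appropriate statistical methodologies to determine comparability of treatment groups pre-operatively". Under Primary Endpoint, the same section gives the five HOOS dimensions a prominent role: "Quality of Life will be important secondary endpoints". The HOOS outcome analysis at the end of Section 6.0 has the sub-scores "compared using parametric or non-parametric techniques (as appropriate) at 6 weeks, 3, 6 and 12 months post-operatively".

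The data-collection text is as follows.

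- **Section 5.1, pre-operative list.** It includes Harris Hip Score elements, x-rays, "Pre-op hematocrit and hemoglobin" and a timed walking test. HOOS is absent.
- **Section listing HOOS.** HOOS is listed under the heading "5.3 Post-operative Data".
- **Visit schedule (after Section 5.4).** The introductory sentence names a pre-operative visit: "Post-operative visit schedule will consist of the following: pre-op, operative, and post-operatively at 2 weeks". The table below it starts at 2 weeks. HOOS appears in four rows, for example at 6 months: "Average Pain Score (VAS) Harris Hip Score HOOS".
- **Section 2.0.** HOOS is mentioned with no time point. A general sentence reads "Data to be collected includes, but is not limited to that specified in Section 5.2 below"; Section 5.2 covers operative details.

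**The concern.** The analysis section promises a comparison for which the data-collection sections provide no data. The stated purpose is comparability before surgery, so the sentence cannot be read as referring to post-operative HOOS. Staff who work from the Section 5.1 list and the visit table would not give the questionnaire at the pre-operative visit.

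Three things are at stake: the planned HOOS comparability check, any later report of HOOS change from baseline, and the option of baseline adjustment for an endpoint the plan itself ranks highly. Only the first is in the plan; the other two are possibilities that close without a baseline. The loss is permanent for each patient, because the pre-operative state cannot be measured after the operation.

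**Working it through.** **Tracing HOOS through the protocol**

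| Place | Pre-operative Harris | Pre-operative HOOS |
|---|---|---|
| Section 6.0, baseline comparison | required | required |
| Section 5.1, pre-operative list | listed | not listed |
| Section 5.3 | post-operative only | post-operative only |
| Visit table | no pre-operative row | no pre-operative row |
| Section 2.0 | no time point | no time point |

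The 12 items in Section 5.1 are subject ID, date of birth, gender, height, weight, BMI, side, diagnosis, Harris elements, x-rays, hematocrit/hemoglobin and timed walk. Section 6.0 needs two instruments at baseline and Section 5.1 supplies one. The list and the table read as intact, with no redaction mark, so the gap does not look like an extraction fault.

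**What is and is not affected**

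- Without a data source: one baseline analysis of 5 sub-scores.
- Still valid: 5 sub-scores × 4 time points = 20 post-operative HOOS comparisons, which rest on randomization and need no baseline.
- Unaffected: the primary endpoint, which uses Harris stair and walking items at 6 weeks.

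**Precision forgone without a baseline HOOS**

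This describes an option the plan could have had; the plan proposes no baseline-adjusted HOOS analysis. The contradiction does not depend on these figures.

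Inputs: 44 per group with 10% attrition (Section 6.0, Sample Size Determination) gives 44 × 0.9 = 39.6, or about 40 evaluable per group, which agrees with the plan's own 40. Two-sided 5% level. Baseline/follow-up correlation ρ of 0.3 to 0.6 is assumed.

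Unadjusted comparison, in SD units:

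- SE = √(2/40) = 0.2236
- 95% CI half-width = t(0.975; 78 df) × SE = 1.991 × 0.2236 = 0.445
- Difference detectable with 80% power (noncentral t) = 0.634

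With the baseline as a covariate, the residual SD is multiplied by √(1 − ρ²), the variance falls by ρ², and the degrees of freedom drop to 77. The half-width is 1.991 × 0.2236 × √(1 − ρ²).

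| ρ (assumed) | √(1 − ρ²) | Variance reduction | CI half-width (SD) | 80% power at (SD) |
|---|---|---|---|---|
| none (unadjusted) | 1 | 0% | 0.445 | 0.634 |
| 0.3 | 0.954 | 9% | 0.425 | 0.605 |
| 0.5 | 0.866 | 25% | 0.386 | 0.549 |
| 0.6 | 0.800 | 36% | 0.356 | 0.508 |

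**The case against.** The strongest reply is that this is one missing list item in a single-center study whose own analysis section names pre-operative HOOS. The intent is plain, and the general sentence in Section 2.0 shows that the lists are not exhaustive. The missing pre-operative row proves little by itself, since Harris and the timed walk have no such row either and are clearly collected before surgery. The case report forms are not among the documents, so whether HOOS was in fact collected cannot be judged. The affected analysis is a descriptive check in a randomized trial, and no conclusion hangs on it. The precision figures describe an adjustment the plan never proposes.

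Much of this stands. The documents show an omission from the lists; they do not show that the data were never collected. The visit table is supporting evidence only, and the weight falls on Section 5.1, which names one of the two required instruments and omits the other. The precision figures do not measure the contradiction.

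The reply does not remove the point. The open-ended sentence in Section 2.0 refers to operative data and instructs nobody to give a questionnaire before surgery. An intention stated only in the statistical section is a weak safeguard for a measurement that cannot be taken later.

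**Conclusion.** The concern holds. Section 6.0 and the data-collection sections contradict each other: one planned baseline analysis of five sub-scores has no specified data source. It should be fixed, but it does not threaten the trial. The primary endpoint and the 20 post-operative HOOS comparisons stand, and the pre-operative Harris elements and timed walk give a partial check on baseline pain and function.

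The forgone gain from baseline adjustment is a confidence interval about 5% to 20% narrower (0.425/0.445 = 0.955; 0.356/0.445 = 0.80). That rests on 40 evaluable patients per group and an assumed correlation of 0.3 to 0.6. The textual contradiction rests on no assumption beyond the lists being complete as shown.

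**What to change.** Add HOOS, all five sub-scales, to Section 5.1, and add a pre-operative row containing HOOS to the visit table. In Section 6.0, state that each post-operative HOOS sub-score is compared with its pre-operative value as a covariate. The first step resolves the contradiction; the covariate is an improvement that the baseline makes possible.

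The documents do not give enrolment status, so two further cases need a rule:

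- **Some patients already operated on without a baseline HOOS.** Use the pre-operative Harris pain and function elements as the covariates for all patients, so that there is one model and nobody leaves the Intent-to-Treat comparison.
- **Enrolment complete and no baseline HOOS taken.** Delete the pre-operative HOOS comparison and state that no HOOS baseline exists.

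Optionally, record a VAS pain score at the same pre-operative visit; its absence contradicts nothing in the plan.

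The cost is one short self-completed questionnaire for at most 88 patients at a visit the protocol already names, one case report form page and a minor amendment. The downside is a small added burden on patients at that visit.

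### Optional improvement: a pre-specified Boschloo exact test would never reject less often than Fisher's test on the primary endpoint and would usually gain a few points of power at no patient cost

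*Combined protocol and SAP*

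**What the plan says.** All of this is in section 6.0 of the combined protocol and SAP.

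- **Analyses Planned:** the 6-week proportion "as evaluated with the Harris Hip Evaluation at 6 weeks post-operatively will be compared using a 2-tailed Fisher's Exact test".
- **Sample Size Determination:** the same test is used. Historical anterior-approach patients able to "climb stairs normally, and walk unlimited, were 37%, and 40% respectively". With a 30% difference and 85% power, "the required sample size for this study is 40 patients per treatment group". Then "To account for 10% attrition the sample size was increased to 44 patients per treatment group", 88 in total.
- **Treatment Assignment:** the schedule will "utilize blocks to ensure approximate treatment balance at any time during the study enrollment phase", so exactly equal arms are not promised.
- **Analysis Populations:** "The Intent-to-Treat population will be analyzed". How a patient without a 6-week outcome enters the analysis is not stated.
- **Alpha:** none is given for the primary test. The only threshold, "with $p \leq 0.05$ being considered significant", belongs to the complications comparison at the end of the section.

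**The concern.** Fisher's test conditions on the total number of successes. Because the table is discrete, it can rarely spend the full 5%. In a trial of 88 patients that rests on one 2x2 comparison, the unspent error rate is lost power.

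An unconditional exact test can recover part of it without extra patients, visits or data, and without going above 5%. What is at stake is a few points of power and the reading of borderline tables. At 44/44, for example, 20 vs 11 successes (45% vs 25%) is not significant with Fisher's test (p = 0.073) but is with Boschloo's (p = 0.048).

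**Working it through.** **Inputs.** From section 6.0: 40 per arm before and 44 after attrition; 37% and 40%; a 30-point difference with no direction given; 85% power; 10% attrition. Assumed: two-sided alpha 0.05, and any rate other than those implied by 37%, 40% and the 30 points. No rate is given for the combined (either/or) endpoint. With components of 37% and 40% it lies between 40% and 37 + 40 = 77%. If the two were independent it would be 1 − 0.63 × 0.60 = 62%.

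**Formulas.** For arm sizes n1, n2 and rejection region R:

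- Power = sum over (x, y) in R of Bin(x; n1, p1) × Bin(y; n2, p2).
- Maximum size = the largest value of that sum over a common rate p1 = p2 = p.
- Fisher: R = {two-sided Fisher p ≤ 0.05}.
- Boschloo: R = {two-sided Fisher p ≤ c}, with c the largest cut-off whose maximum size is at most 0.05. Fisher's own size is at most 0.05, so c is at least 0.05 and this region must contain Fisher's.

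**Step 1: the plan's own figure.** For 40% vs 10%, full enumeration gives Fisher power of 85.2% at 40/40, and 40 is the smallest size per arm reaching 85%. The plan's figure is reproduced; 40 × 1.1 = 44. In the other direction (37 vs 67 or 40 vs 70) Fisher needs 52 per arm.

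**Step 2: unused error rate.**

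| Arms | Fisher max size | Boschloo max size |
|---|---|---|
| 40/40 | 3.30% | 4.77% |
| 44/44 | 3.06% | 4.78% |
| 43/45 | 3.97% | 4.97% |
| 42/46 | 3.99% | 4.82% |
| 41/44 | 4.05% | 4.70% |
| 40/43 | 4.75% | 4.89% |

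At 44/44 the Boschloo cut-off is c = 0.0734, which adds 62 tables. Two of them are 20 vs 11 (Fisher 0.0734, Boschloo 0.0478) and 27 vs 17 (0.0544, 0.0422).

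**Step 3: power, Fisher to Boschloo.** The completers column averages over arm sizes that are independent Bin(44, 0.9).

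| Rates (%) | 44/44, all observed | Completers, 10% random dropout |
|---|---|---|
| 40 vs 10 | 87.9 → 92.0 | 86.6 → 88.8 |
| 37 vs 7 | 91.5 → 94.6 | 90.4 → 92.1 |
| 50 vs 20 | 80.2 → 84.9 | 77.3 → 80.8 |
| 55 vs 25 | 77.0 → 81.8 | 75.3 → 77.9 |
| 62 vs 32 | 73.6 → 79.9 | 74.2 → 75.4 |
| 37 vs 67 | 73.4 → 79.8 | 74.2 → 75.3 |
| 40 vs 70 | 74.2 → 80.1 | 74.4 → 75.9 |

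The gain is 3.1 to 6.4 points with complete data and 1.1 to 3.45 under dropout. In the dropout column, the chance that the realised arm sizes give a gain under 0.5 points is 42% to 56% for the last three pairs.

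**Step 4: missing counted as not able (assumption, 10% missing in each arm).** Each rate is multiplied by 0.9 at 44/44, so 40 vs 10 becomes 36 vs 9. Power goes from 82.3% to 87.7% for 40 vs 10, 87.0% to 91.2% for 37 vs 7, 65.2% to 71.5% for 62 vs 32, and 62.7% to 70.4% for 40 vs 70. Over the seven pairs the gain is 4.2 to 7.7 points.

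**Step 5: where the gain shrinks.** Here the first-named arm has the first-named rate. With all 88 observed, the gain over the seven pairs is 0.1 to 4.6 points at 43/45 and 0.95 to 5.1 at 42/46. It is 0.00 at 41/44 for 40 vs 10. Near the boundary (70 vs 100) it is 0.2 at 44/44 complete and 0.4 under dropout.

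**Step 6: the ordering matters.** Doubling the one-sided Boschloo p-value is a different test. At 40/43 it fails to reject 6 tables that Fisher rejects, and its power for 40 vs 70 is 78.8% against Fisher's 79.8%.

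**The case against.** The strongest reply is that this is preference. Fisher's test is valid, familiar, consistent with the sample size, and meets 85% in the scenario that reproduces the plan (40 vs 10), where it still averages 86.6% under random dropout. That stands, and it is why the point is optional.

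The larger gains need exactly equal arms. For 40 vs 10 the gain is 4.05 points at 44/44 but 0.51 at 43/45. The contrast of 82.3% with 87.7% on either side of the target also depends on that balance: at 43/45, with missing counted as not able, the figures are 87.1% and 87.5%. This also stands, and the quoted ranges should be read as ranges over the listed rate pairs, not over every possible case.

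Where power is shortest, the test does not fix it. The composite rate, the direction of the difference and the rule for missing outcomes matter more than the choice of test. That is true, but those gaps are separate and do not argue against a change that cannot lose power at given arm sizes.

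Finally, Fisher's test would remain for complications and for the sample size. That does no harm: a sample size computed for Fisher's test is merely conservative for Boschloo's.

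**Conclusion.** The point holds as a cheap, optional improvement; it is not an error in the plan. At any given arm sizes the Boschloo test ordered by the two-sided Fisher p-value keeps type I error at or below 5% and cannot have less power than Fisher's test.

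The likely benefit is a few points: the complete-data gains at 44/44 are the favourable case, and the random-dropout average is the more realistic one for a completers analysis. It does not restore 85% under less favourable composite rates. At 62 vs 32 it reaches 79.9% with complete data and 75.4% under dropout.

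The conclusion rests on an assumed two-sided alpha of 0.05, on assumed composite rates, and on which reading of missing 6-week outcomes applies. That the test never loses power against Fisher's does not depend on the rates or on the reading of missing outcomes.

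**What to change.** Before any outcome comparison is seen, replace the primary-test sentence under Analyses Planned with wording such as:

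> The primary comparison uses the two-sided Boschloo exact unconditional test at two-sided alpha 0.05, with tables ordered by the two-sided Fisher p-value at the arm sizes analysed. Fisher's exact test is reported as a sensitivity analysis.

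The ordering must be written down so that the doubled one-sided version is not run by mistake. This wording also settles the primary alpha. It does not settle how missing 6-week outcomes enter, which needs its own rule because it determines the arm sizes analysed.

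Cost: two or three SAP lines and a short validated program, or software confirmed to use this ordering. No added patients, visits or data. Downsides: a less familiar test, the risk of the wrong variant, and little or no gain for some arm sizes and rates.
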